1.5.2 Ritonavir

The most frequent clinical and laboratory adverse events reported in subjects who received RTV as monotherapy or in combination with nucleoside analogues include asthenia, nausea, vomiting, abdominal pain, and diarrhea.¹³ Laboratory abnormalities reported with the use of RTV include elevations in hepatic transaminase levels, nonfasting triglyceride, cholesterol, creatine phosphokinase, and uric acid. The frequency of adverse events following administration of low dose RTV (100 mg QD) is not well known. However, it is expected that the incidence of adverse events with this low dose would be reduced. Subjects in the current study will be monitored for all adverse events and clinical laboratory abnormalities.

2 STUDY OBJECTIVES

2.1 Primary Objective

The primary objective of this study is to assess the antiviral activity of BMS-626529 following administration of selected regimens of BMS-663068 with and without RTV administered orally to HIV infected subjects for 8 days.

2.2 Secondary Objectives

Secondary objective(s):

- To assess safety and tolerability of multiple regimens of BMS-663068 with and without RTV in HIV infected subjects
- To assess the effect of BMS-626529 following multiple regimens of BMS-663068 on CD4+ and CD8+ lymphocyte counts and percents
- To assess the PK of BMS-626529 following multiple regimens of BMS-663068 with and without RTV in HIV infected subjects
- To assess the diurnal variation in the PK exposures of BMS-626529 following multiple regimens of BMS-663068 with and without RTV in HIV infected subjects
- To assess the plasma protein binding for BMS-626529

- To assess the relationships between change from baseline in \log_{10} HIV RNA versus Inhibitory Quotient (IQ) and PK exposures for BMS-626529 following multiple regimens of BMS-663068 with and without RTV
- To assess the PK of RTV when coadministered with various regimens of BMS-663068

2.3 Exploratory Objectives

- To explore the effect of BMS-626529 following multiple regimens of BMS-663068 with and without RTV on activated (DR+) CD4+ and CD8+ subsets
- To explore the effect of BMS-626529 following multiple regimens of BMS-663068 with and without RTV on neutralizing antibody activity
- To explore the effect of BMS-626529 following multiple regimens of BMS-663068 with and without RTV on HIV co-receptor usage (CCR5 versus CXCR4) and to explore the relationship between HIV co-receptor usage and antiviral activity
- To explore the difference in antiviral activity of BMS-626529 following multiple regimens of BMS-663068 with and without RTV by prior antiretroviral (ARV) treatment history (ARV naive versus ARV experienced)
- To explore the change in viral susceptibility measured by envelope genotype and phenotype

3 ETHICAL CONSIDERATIONS

3.1 Good Clinical Practice

This study will be conducted in accordance with Good Clinical Practice (GCP), as defined by the International Conference on Harmonisation (ICH) and in accordance with the ethical principles underlying European Union Directive 2001/20/EC and the United States Code of Federal Regulations, Title 21, Part 50 (21CFR50).

The study will be conducted in compliance with the protocol. The protocol and any amendments and the subject informed consent will receive Institutional Review Board/Independent Ethics Committee (IRB/IEC) approval/favorable opinion prior to initiation of the study.

All potential serious breaches must be reported to BMS immediately. A serious breach is a breach of the conditions and principles of GCP in connection with the study or the protocol, which is likely to affect, to a significant degree, the safety or physical or mental integrity of the subjects of the study or the scientific value of the study.

Study personnel involved in conducting this study will be qualified by education, training, and experience to perform their respective task(s).

This study will not use the services of study personnel where sanctions have been invoked or where there has been scientific misconduct or fraud (eg, loss of medical licensure, debarment).

Systems with procedures that assure the quality of every aspect of the study will be implemented.

3.2 Institutional Review Board/Independent Ethics Committee

Before study initiation, the investigator must have written and dated approval/favorable opinion from the IRB/IEC for the protocol, consent form, subject recruitment materials/process (eg, advertisements), and any other written information to be provided to subjects. The investigator or sponsor should also provide the IRB/IEC with a copy of the Investigator Brochure or product labeling, information to be provided to subjects and any updates.

The investigator or sponsor should provide the IRB/IEC with reports, updates and other information (eg, expedited safety reports, amendments, and administrative letters) according to regulatory requirements or institution procedures.

3.3 Informed Consent

Investigators must ensure that subjects are clearly and fully informed about the purpose, potential risks, and other critical issues regarding clinical studies in which they volunteer to participate. Freely given written informed consent must be obtained from every subject prior to clinical study participation, including informed consent for any screening procedures conducted to establish subject eligibility for the study.

The rights, safety, and well-being of the study subjects are the most important considerations and should prevail over interests of science and society.

[Appendix 1](#) contains BMS procedures on obtaining informed consent from all subjects, prior to participating in a clinical study. The relevant procedures must be used whenever they are applicable (see subject selection criteria in Sections [4.2.1](#) and [4.2.2](#)).

Informed consent given by legally acceptable representatives or witnesses is **not** permitted in this study.

4 INVESTIGATIONAL PLAN

4.1 Study Design and Duration

This is a randomized, open label, multiple-dose parallel study. Subjects will undergo screening evaluations to determine eligibility within 35 days prior to study enrollment. Subjects will be admitted to the clinical facility the evening prior to dosing (Day -1). Subjects will be randomized into one of 5 regimen groups: Group 1 - BMS-663068 600 mg Q12H + RTV 100 mg Q12H; Group 2 - BMS-663068 1200 mg QHS + RTV 100 mg QHS; Group 3 - BMS-663068 1200 mg Q12H + RTV 100 mg Q12H; Group 4 - BMS-663068 1200 mg Q12H + RTV 100 mg QAM; Group 5 - BMS-663068 1200 mg Q12H.

Each regimen group will consist of 10 subjects. Subjects in each regimen will be randomized and stratified by prior antiretroviral treatment history (ARV naive versus ARV experienced). ARV naive is defined as; no prior ARV therapy of ≥ 1 week. Each regimen group will contain approximately the same distribution of ARV naive and ARV experienced subjects. No more than 70% of the total population (or within each regimen group) will be ARV naive or ARV experienced. All regimen groups may initiate dosing simultaneously. Subjects will be confined to the clinical facility until Day 11. Subjects will return to the unit on Day 15 for a follow-up visit and on Day 50 for discharge procedures. Subjects may have a ± 3 day window around the discharge visit day (Day 50). Safety assessments consisting of ECGs, vital signs, physical exams and clinical laboratory tests will be conducted at screening and at selected time points throughout the study.

All doses will be administered under fed conditions. Subjects in Group 2 (QHS regimen group) will receive study drug every 24 hours in the evening (PM) from Day 1 to Day 8. Subjects in Group 4 (RTV QAM regimen group) will receive BMS-663068 every 12 hours and RTV every 24 hours in the morning (with BMS-663068) from Day 1 to Day 8. Subjects in Groups 1, 3 and 5 (Q12H regimen group) will receive study drug every 12 hours from Day 1 to Day 8.

Plasma HIV RNA levels will be measured pre-AM drug administration on the mornings of Day 1 to Day 8 in groups 1, 3, 4 and 5 and Pre-PM drug administration in group 2. On days when dose is not administered, sample collection time should be maintained. Serial blood samples for pharmacokinetic determinations will be obtained on Days 1 and 8-11. Blood samples for trough concentrations will be obtained on Days 5 through 7 prior to morning study drug administrations (prior to evening administration for Group 2, QHS regimen group) for C_{trough} and steady-state assessment. In addition, blood samples for protein binding assay will be collected at specified timepoints throughout the study and selected regimen groups will be analyzed.

Blood for CD4⁺ and CD8⁺ lymphocyte counts and percents and activated (DR⁺) CD4⁺ and CD8⁺ subsets, genotyping, phenotyping, HIV co-receptor usage (CCR5 versus CXCR4), exploratory resistance analysis, measurement of neutralizing antibody activity will be collected at specified timepoints throughout the study. These samples may be analyzed if deemed relevant. Screening samples for population RT/Pol genotyping to confirm that all subjects are infected with clade B HIV will be analyzed in all enrolled subjects. Day 1 predose samples for envelope phenotyping will be collected and analyzed for all randomized subjects.

Approximately 800 mL of blood will be drawn from each subject during the study.

The approximate duration of the study is 88 days. Study participation includes a 35-day screening period, 8-day treatment and 2 follow-up visits.

End of the study will be the date of the last visit of the last subject undergoing the study. Last visit will be the last follow-up visit of a subject.

At the end of the study, the sponsor will not continue to supply study drug to subjects/investigators unless the sponsor chooses to extend the study. The investigator should ensure that the subject receives appropriate standard of care to treat the condition under study.

Table 4.1 summarizes the study design and study parameters.

Table 4.1: AI438006 Study Design

	Regimen Group 1 (N=10)	Regimen Group 2 (N=10)	Regimen Group 3 (N=10)	Regimen Group 4 (N=10)	Regimen Group 5 (N=10)
Dose and Regimen	600 mg BMS- 663068 Q12H + 100 mg RTV Q12H	1200 mg BMS- 663068 QHS + 100 mg RTV QHS	1200 mg BMS- 663068 Q12H + 100 mg RTV Q12H	1200 mg BMS- 663068 Q12H + 100 mg RTV QAM	1200 mg BMS- 663068 Q12H
Days subjects receive BMS-663068	Day 1-8				
In-patient Days	Day -1 to Day 11				
Furlough from clinical unit	Day 11				
Out-patient visits	Day 15 and (Day 50 +/- 3 days)				
Discharge from Study	Day 50 +/- 3 days				

4.2 Study Population

For entry into the study, the following criteria MUST be met prior to dosing on Day 1.

No exceptions will be granted.

4.2.1 Inclusion Criteria

1) Signed Written Informed Consent

- a) The signed informed consent form

2) Target Population

- a) Clade B HIV-1 infected subjects meeting the following criteria at the screening visit (within 35 days of enrollment):
 - i) Plasma HIV RNA level \geq 5,000 copies/mL (may be repeated for confirmation)
 - ii) Antiretroviral naive or experienced (ARV naive is defined by: No prior antiretroviral therapy of \geq 1 week)

- iii) CD4+ lymphocyte measurement ≥ 200 cells/ μ L (may be repeated for confirmation)
 - iv) Off all antiretroviral therapy with HIV activity for ≥ 8 weeks
 - v) Have not previously received an HIV attachment inhibitor
- b) Body Mass Index (BMI) of 18 to 35 kg/m², inclusive. BMI = weight (kg)/ [height (m)]²
- c) Not currently co-infected with HCV or HBV

3) Age and Sex

- a) Men and women, ≥ 18 years of age

Women of childbearing potential (WOCBP) must be using an adequate method of contraception (generally defined as two separate forms of contraception, one of which must be an effective barrier method (eg, condom with spermicide), to avoid pregnancy throughout the study and for up to 12 weeks after the last dose of investigational product in such a manner that the risk of pregnancy is minimized.

WOCBP include any female who has experienced menarche and who has not undergone successful surgical sterilization (hysterectomy, bilateral tubal ligation, or bilateral oophorectomy) or is not postmenopausal. Post menopause is defined as:

- Amenorrhea ≥ 12 consecutive months without another cause or
- For women with irregular menstrual periods and on hormone replacement therapy (HRT), a documented serum follicle stimulating hormone (FSH) level > 35 mIU/mL

Women who are using oral contraceptives, other hormonal contraceptives (vaginal products, skin patches, or implanted or injectable products), or mechanical products such as an intrauterine device or barrier methods (diaphragm, condoms, spermicides) to prevent pregnancy, or are practicing abstinence or where their partner is sterile (eg, vasectomy) should be considered to be of childbearing potential.

WOCBP must have a negative serum or urine pregnancy test (minimum sensitivity 25 IU/L or equivalent units of HCG) within 24 hours prior to the start of investigational product.

4.2.2 Exclusion Criteria

1) Sex and Reproductive Status

- a) WOCBP who are **unwilling or unable** to use an acceptable method to avoid pregnancy (generally defined as two effective forms of contraception) for the entire study period and for up to 12 weeks after the last dose of investigational product.
- b) WOCBP using a prohibited contraceptive method including oral, injectable, or implantable hormonal contraceptive agent within 12 weeks of enrollment.
- c) Women who are pregnant or breastfeeding.
- d) Women with a positive pregnancy test on enrollment or prior to investigational product administration.
- e) Sexually active fertile men not using effective birth control (generally defined as two effective forms of contraception) during study participation and for at least 12 weeks after the last dose of investigational product if their partners are WOCBP.

2) Medical History and Concurrent Diseases

- a) Any significant acute or chronic medical illness which is not stable or is not controlled with medication or not consistent with HIV infection.
- b) Current or recent (within 3 months) gastrointestinal disease that, in the opinion of the Investigator or Medical Monitor, may impact on drug absorption and/or put the subject at risk for GI tract irritation and/or bleeding. Exclusionary diseases include, but are not limited to gastrointestinal ulcers, esophageal or gastric varicities, or hematochezia.
- c) Acute diarrhea lasting ≥ 1 day, within 3 weeks prior to randomization. Diarrhea will be defined as the passage of liquid feces and/or a stool frequency greater than three times per day.
- d) Any major surgery within 4 weeks of study drug administration.
- e) Any gastrointestinal surgery that could impact upon the absorption of study drug.
- f) Donation of blood or plasma to a blood bank or in a clinical study (except a Screening visit or follow up visit of less than 50 mL) within 4 weeks of study drug administration.
- g) Blood transfusion within 4 weeks of study drug administration.
- h) Inability to tolerate oral medication.
- i) Inability to be venipunctured and/or tolerate venous access.
- j) A personal history of clinically relevant cardiac disease, symptomatic or asymptomatic arrhythmias, syncopal episodes, or additional risk factors for torsades de pointes.

- k) A personal or family history of long QT syndrome.
- l) Subjects who are **unwilling** to practice adequate infection protection during and after study participation to minimize potential for spread of HIV infection, including HIV which may have developed resistance to HIV attachment inhibitors. Such protections could include, but are not limited to behaviors to minimize potential for exposure to the subjects' bodily fluids or initiation of HAART therapy if indicated and recommended by a physician.
- m) Recent (within 6 months) drug or alcohol abuse as defined in DSM IV, Diagnostic Criteria for Drug and Alcohol Abuse ([Appendix 2](#)).
- n) Any other medical, psychiatric and/or social reason which, in the opinion of the Investigator, would make the candidate inappropriate for participation in this study.

3) Physical and Laboratory Test Findings

- a) Evidence of organ dysfunction or any clinically significant deviation from normal in physical examination, vital signs, ECG or clinical laboratory determinations or not consistent with the subject's degree of HIV infection.
- b) Confirmed QT value > 500 msec at screening or Day -1.
- c) Confirmed QTc value > 470 msec for women and > 450 msec for men at screening or Day -1.
- d) Evidence of second or third degree heart block at screening or Day -1, confirmed by repeat ECG.
- e) Positive urine screen for drugs of abuse at either Screening or Day -1 without a valid prescription (subjects positive for cannabinoids and/or amphetamines will be included, unless excluded by exclusion criteria 2m in Section [4.2.2](#)).
- f) Positive blood screen for hepatitis B surface antigen.
- g) Positive blood screen for hepatitis C antibody and hepatitis C RNA.
- h) Any of the following screening or Day -1 laboratory results outside of the ranges specified below as defined by the central laboratory, confirmed by repeat analysis.
 - i) Absolute Neutrophil Count (ANC) 0.7 x lower limit of normal (LLN)
 - ii) Hemoglobin 0.8 x LLN
 - iii) ALT > 3 x upper limit of normal (ULN)
 - iv) Creatinine clearance (as estimated by method of Cockcroft and Gault¹⁸) less than 60 mL/min.

4) Allergies and Adverse Drug Reactions

- a) History of allergy to an HIV attachment inhibitor.
- b) History of allergy to HIV protease inhibitor (e.g. RTV).
- c) History of any significant drug allergy (such as anaphylaxis or hepatotoxicity).

5) Prohibited Treatments and/or Therapies

- a) Prior exposure to an HIV attachment inhibitor (including BMS-488043 or BMS-663068).
- b) Exposure to any investigational drug or placebo within 4 weeks of study drug administration.
- c) Use of any prescription drugs within 4 weeks prior to study drug administration. However, certain drugs may be allowed if approved by the BMS medical monitor.
- d) Use of any other drugs, including over-the-counter medications, vitamins and/or herbal preparations (eg. St. John's wort), within 1 week prior to study drug administration. However, certain drugs may be allowed if approved by the BMS medical monitor.
- e) Use of an oral, injectable or implantable hormonal contraceptive agent within 12 weeks of study drug administration.
- f) Use of any prescription drugs or OTC drugs that may cause GI tract irritation or bleeding (ie, NSAIDs, aspirin) within 2 weeks of study drug administration, unless approved by the BMS medical monitor.
- g) Use of alcohol-containing beverages within 3 days prior to study drug administration.
- h) Use of grapefruit or grapefruit-containing products or Seville orange-containing products within 7 days prior to study drug administration.

6) Other Exclusion Criteria

- a) Prisoners or subjects who are involuntarily incarcerated.
- b) Subjects who are compulsorily detained for treatment of either a psychiatric or physical (eg, infectious disease) illness.

Eligibility criteria for this study have been carefully considered to ensure the safety of the study subjects and to ensure that the results of the study can be used. It is imperative that subjects fully meet all eligibility criteria.

4.2.3 Discontinuation of Subjects from Treatment

Subjects MUST discontinue investigational product (and noninvestigational product at the discretion of the investigator) (investigational or noninvestigational treatment) for any of the following reasons:

- Withdrawal of informed consent (subject's decision to withdraw for any reason)
- Any clinical adverse event (AE), laboratory abnormality or intercurrent illness which, in the opinion of the investigator, indicates that continued participation in the study is not in the best interest of the subject
- Pregnancy (see Section 7.6.2)
- Termination of the study by Bristol-Myers Squibb (BMS)
- Loss of ability to freely provide consent through imprisonment or involuntarily incarceration for treatment of either a psychiatric or physical (eg, infectious disease) illness
- Inability to comply with protocol
- Discretion of the investigator
- Clinically relevant ventricular arrhythmia including torsades de pointes
- Confirmed QTcB or QTcF value > 500 msec
- Type 2 (Mobitz II) second or third-degree heart block (confirmed by repeat ECG)
- New onset of clinically relevant gastrointestinal bleeding
- New onset of signs and symptoms of severe persistent gastrointestinal irritation (such as abdominal pain) deemed unrelated to another etiology

All subjects who discontinue should comply with protocol specified follow-up procedures as outlined in Section 6. The only exception to this requirement is when a subject withdraws consent for all study procedures or loses the ability to consent freely (ie, is imprisoned or involuntarily incarcerated for the treatment of either a psychiatric or physical illness).

If a subject was withdrawn before completing the study, the reason for withdrawal must be entered on the appropriate case report form (CRF) page.

Dosing within a regimen group will be stopped and the study halted until safety information can be reviewed in the event of the following situations:

- Two or more subjects within a regimen group experience new onset of QTcF values >500 msec following dosing (confirmed by repeat ECG)
- Two or more subjects within a regimen group experience second-degree Mobitz II or third-degree heart block (confirmed by a repeat ECG)
- Clinically relevant ventricular arrhythmia including torsades de pointes in any subject in a given dose panel
- Two or more subjects within a regimen group experience new onset of clinically relevant gastrointestinal bleeding
- Two or more subjects within a regimen group experience new onset of signs and symptoms of severe persistent gastrointestinal irritation (such as abdominal pain) deemed unrelated to another etiology
- Two or more subjects within a regimen group experience the same drug-related severe clinical or laboratory adverse event

The study may be terminated prematurely if:

- The Sponsor, in consultation with the Principal Investigators, feels that the number and/or severity of AEs justifies discontinuation of the study.
- The Sponsor considers the applied doses of the study drug to be no longer relevant.
- The Sponsor decides to discontinue the study.
- Data not known before become available and raise concern about the safety of the study drug so that continuation would pose potential risks to the subjects.

Premature termination of the study must be documented and clinical study results will be reported according to the requirements outlined in this protocol as far as applicable.

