7 ADVERSE EVENTS

7.1 Definitions

An *Adverse Event (AE)* is defined as any new untoward medical occurrence or worsening of a pre-existing medical condition in a patient or clinical investigation subject administered an investigational (medicinal) product and that does not necessarily have a causal relationship with this treatment. An AE can therefore be any unfavorable and unintended sign (including an abnormal laboratory finding, for example), symptom, or disease temporally associated with the use of investigational product, whether or not considered related to the investigational product.

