7.2 Assignment of Adverse Event Intensity and Relationship to Study Drug

The following categories and definitions of intensity as determined by a physician should be used for all BMS clinical study AEs:

- Mild (Grade 1) - Awareness of event but easily tolerated
- Moderate (Grade 2) - Discomfort enough to cause some interference with usual activity
- Severe (Grade 3) - Inability to carry out usual activity
- Very Severe (Grade 4) - Debilitating, significantly incapacitates subject despite symptomatic therapy

The following categories and definitions of causal relationship to study drug as determined by a physician should be used for all BMS clinical study AEs:

- Related: There is a reasonable causal relationship to study drug administration and the AE
- Not related: There is not a reasonable causal relationship to study drug administration and the AE

The expression "reasonable causal relationship" is meant to convey in general that there are facts (eg, evidence such as de-challenge/re-challenge) or other arguments to suggest a positive causal relationship.

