7.4 Laboratory Test Abnormalities

All laboratory test values captured as part of the study should be recorded on the appropriate laboratory test results pages of the CRF, or be submitted electronically from a central laboratory. In addition, the following laboratory abnormalities should also be captured on the nonserious AE CRF page (paper or electronic) or SAE paper CRF page as appropriate:

- Any laboratory test result that is clinically significant or meets the definition of an SAE
- Any laboratory abnormality that required the subject to have study drug discontinued or interrupted
- Any laboratory abnormality that required the subject to receive specific corrective therapy

It is expected that wherever possible, the clinical, rather than the laboratory term would be used by the reporting investigator (eg, anemia versus low hemoglobin value).

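### The halt rule counts severe laboratory adverse events, but the only severity scale is functional, so read literally a symptom-free marked laboratory abnormality does not count

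*Protocol*

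**What the plan says.** Section 4.2.3 lists six situations in which dosing within a regimen group stops and the study is halted until safety information has been reviewed. The last is "Two or more subjects within a regimen group experience the same drug-related severe clinical or laboratory adverse event".

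Section 7.1 makes abnormal laboratory findings adverse events. Section 7.4 says which ones are recorded as such, beginning with "Any laboratory test result that is clinically significant or meets the definition of an SAE"; the other routes are that the abnormality led to stopping or interrupting study drug, or needed corrective therapy.

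Severity is set in section 7.2, which opens: "The following categories and definitions of intensity as determined by a physician should be used for all BMS clinical study AEs". The third category is "Severe (Grade 3) - Inability to carry out usual activity". The fourth, very severe, is also defined by incapacity. Section 7.2 likewise supplies "definitions of causal relationship to study drug as determined by a physician".

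No value-based severity grade for laboratory results appears in the protocol. The ANC, hemoglobin, ALT and creatinine clearance limits in section 4.2.2 are entry criteria. The CK limit of twice the upper limit of normal in section 6.3.7 only prompts a troponin test. Section 1.3.4.1 mentions marked abnormalities in an earlier study, but the term is not defined here or tied to the halt.

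**The concern.** The rule asks for a severity grade that the stated scale cannot sensibly give to a laboratory value. A rise in transaminases or CK often has no symptoms, so a subject can have a large one and still do everything they normally do. Under section 7.2 as worded, that event is not severe.

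This is one of the protocol's mandatory group-level stops, and laboratory effects are a foreseeable risk. Section 1.5.2 reports transaminase and creatine phosphokinase elevations with ritonavir, which is given in four of the five groups, although it expects fewer events at this low dose. Section 1.3.2 reports bilirubin increases in dogs given 100 mg/kg/day or more of BMS-663068 for a month. At stake is whether two matching laboratory events in a group of 10 would reliably bring about the review that section 4.2.3 promises.

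**Working it through.** The main check compares definitions.

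1. The rule (4.2.3) needs two subjects in one group with the same event, and that event must be drug-related and severe. Laboratory events are expressly included.
2. The scale (7.2) is stated for all adverse events, with no exception for laboratory findings. Grades 3 and 4 are both functional.
3. Literal result: a symptom-free laboratory abnormality of any size is below Grade 3 and adds nothing to the count of two.
4. Looser result: section 7.2 leaves the grade to a physician. Section 1.3.4.6 describes CK elevations in an earlier study as severe and very severe, and says that the two subjects with myalgia had no CK elevation. This suggests grading by value, but no scale is stated there and none is carried into this protocol. With approximately 6 centers (Synopsis), the two subjects who must match may be graded by different physicians using different cut-offs.
5. Comparison with the other triggers: two of the six are read from an ECG, for example "Two or more subjects within a regimen group experience new onset of QTcF values >500 msec following dosing (confirmed by repeat ECG"). The other four rest wholly or partly on judgement, for example "Two or more subjects within a regimen group experience new onset of clinically relevant gastrointestinal bleeding". Laboratory severity resembles the first kind, since it can be read from a measured value.

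The protocol gives no probability for the halt rule. The nearest figure is in section 8.1: an 80% chance of seeing at least one case of an event with 15% incidence among 10 subjects. It reproduces: 1 − 0.85^10 = 0.803.

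The same binomial set-up shows how often a value-based trigger could fire. The inputs are 10 subjects per group, a threshold of 2 and five groups, all from the protocol, and an **assumed** true incidence r of one drug-related abnormality of Grade 3 or higher, since the protocol gives none.

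Per group: P = 1 − (1 − r)^10 − 10r(1 − r)^9

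- r = 1%: 1 − 0.90438 − 0.09135 = 0.0043, or 0.4%
- r = 5%: 1 − 0.59874 − 0.31512 = 0.0861, or 8.6%

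At least one of five groups, with the same r in each and independence: 1 − (1 − P)^5

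- r = 1%: 1 − 0.99573^5 = 0.021, about 2%
- r = 5%: 1 − 0.91386^5 = 0.363, about 36%

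The study-level figure matters because the rule halts the study as well as the group. If all these cases were symptom-free, the literal section 7.2 reading would count none of them and this trigger would fire with probability 0.

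**The case against.** The strongest reply is that the literal reading is strained. The rule speaks of severe laboratory events, so its author took them to be gradable, and grading is a physician's decision. Section 1.3.4.6 indicates that CK has been graded without the obvious symptom. This stands as a reason to expect uneven grading rather than silence. A reader might infer that the laboratory trigger can never fire; the documents do not support that. The reply does not supply a cut-off, however.

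Second, judgement is not peculiar to this trigger, and the fix leaves two judgements in place: drug-relatedness, and clinical significance as the main route by which a laboratory result becomes an adverse event. That is correct. The fix removes only the mismatch in severity.

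Third, there is other cover. Section 4.2.3 requires a subject to be discontinued when the investigator judges that a laboratory abnormality makes continuing not in that subject's interest. It also lets the sponsor end the study on the number or severity of adverse events, or on new safety data. Section 6.3.7 uses a central laboratory by default and sends all required results to the sponsor. Section 8.5 allows safety data in the interim reviews. A reader might infer that subjects with marked laboratory changes are unprotected; these provisions say otherwise. But individual discontinuation protects one subject, the sponsor's powers are discretionary, and none of these is the automatic two-subject halt.

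Fourth, the rule's reach is short. Dosing ends on Day 8 and samples are taken before dosing, so only the Day 4 and Day 8 scheduled draws fall within a subject's own dosing period. Later results could stop dosing only in other subjects. CK is not drawn after Day 11. This stands and limits the practical effect.

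**Conclusion.** The mismatch is real. A mandatory safety stop uses a severity term whose only stated definition does not fit laboratory findings. Followed literally, the protocol would not count symptom-free marked values; followed loosely, the trigger varies with the grader. The second is likelier, given physician grading and the CK example.

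The severity is low. Sections 1.3.4 and 1.5.1 report no clinically relevant laboratory effects in phase 1, including 10 days of dosing with ritonavir (section 1.3.4.4, preliminary results), so the need is probably rare. No actual halt probability can be derived from the protocol. The 0.4% to 8.6% per group and 2% to 36% study-level figures rest on assumed incidences, a common rate in all five groups and independence. They illustrate the cost of the fix and are not evidence of harm.

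The definition reached does not depend on those figures. It belongs in the protocol, because the halt rule itself is there.

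**What to change.** State in section 4.2.3, with a cross-reference in section 7.2, that for laboratory adverse events *severe* means Grade 3 or higher on a named value-based laboratory toxicity table chosen by the sponsor and applied to the reported results. Keep the functional scale in section 7.2 for clinical adverse events. Drug-relatedness and clinical significance stay with the physician.

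This takes one or two sentences and a table reference in an amendment, with no new tests or visits, because the values are already collected and sent to the sponsor. The downside is that the study may be halted for review more often, on the scale illustrated above. Each such halt is a pause for review and does not by itself end the study.
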